[name]

NCT04938037 UNIQUE PROTOCOL ID: 2021/353

05.05.2020

Comparison of Spinoglenoid Versus Suprascapular Notch Approaches for Ultrasound-Guided Distal Suprascapular Nerve Blocks for Shoulder Pain: A Prospective Randomized Trial

Study Design and Patients

The present study was conducted in a prospective, randomized, double-blind fashion at a tertiary-care university hospital in Kayseri, Turkey, from June 2021 to August 2022. The Consolidated Standards of Reporting Trials (CONSORT) guideline was used as the reference for the standardization of the data reported in this study. Ethical approval for the study was obtained from the Erciyes University Clinical Research Ethics Committee (approval date: May 05, 2020; approval number: 2021/353). The study was also registered at ClinicalTrials.gov (NCT04938037). The research adhered to the Ethical Principles for Medical Research Involving Human Subjects outlined in the World Medical Association's Declaration of Helsinki, as revised in 2013. A written informed consent form approved by the ethics committee was signed by each participant who agreed to participate in the study.

All patients over the age of 18 who had chronic shoulder pain of any specific etiology (duration >3 months), had a visual analog scale (VAS) score above 4 despite conservative treatment, and gave informed written consent were screened for eligibility for the study. Exclusion criteria were previous fractures or surgery around the shoulder, receipt of any injections to the affected shoulder in the last 3 months, chronic pain due to other diseases such as malignancy, cervical radiculopathy, hemiplegia, or uncontrolled diabetes or hypertension, coagulopathies, local infection over the shoulder region, or allergy to local anesthetics.

The clinical diagnosis of chronic shoulder pain for each included patient was determined by physical examination and radiologic imaging technique (magnetic resonance imaging [MRI] or ultrasound [US]).

Patients were randomized into two groups: Group 1 received SSNB at the spinoglenoid notch level, while Group 2 received SSNB at the suprascapular notch level. Stratified randomization was performed in four blocks based on age and gender. Group allocations were made (using sealed envelopes) by our medical secretary. The assigned numbers were presented to the physician at the time the procedure was performed. The patients and the physician assessing the outcomes were blinded to the group assignments, but the physician who performed the injections could not be blinded.

Procedures

All injections were administered by a single experienced physician specializing in musculoskeletal injections who used the linear transducer (LA3-16AD) of the Samsung HM70A Plus US device (Seoul, South Korea). The same injection solutions were prepared for both groups and consisted of 1 mL of methylprednisolone acetate (40 mg/mL) and 5 mL of 0.5% bupivacaine for the SSNB.

For SSNB at the level of the spinoglenoid notch, the patients were positioned on a stretcher in the lateral decubitus position between the US device and the physician. The patient's hand on the side of the injection was placed on the contralateral shoulder. The transducer was positioned on the glenohumeral joint, parallel to the inferior border of the spina scapula, and then shifted medially to visualize the spinoglenoid notch. After sterile prep, a 20G 3.5-inch needle was advanced, using an in-plane technique, into the spinoglenoid notch. A lateral-medial needle insertion was used so that the intended target of the final needle tip was at the medial wall of the spinoglenoid notch.

For SSNB at the level of the suprascapular notch, the technique described by Harmon et al.(1) was used. In brief, the patient was positioned seated between the physician and the US equipment. The patient's injection-side hand was placed on the shoulder on the opposite side. To view the suprascapular notch, the transducer was positioned above the acromion, parallel to the spina scapula, and then gently adjusted medially. After sterile prep, a 20G 3.5-inch needle was advanced into the suprascapular notch.

One week after the injection, all patients received a prescribed exercise regimen to be performed in their own homes. The exercise routine encompassed self-stretching, joint mobility exercises, and strength-building activities. A designated physical therapist demonstrated the exercises to each patient individually, and an exercise booklet was provided to assist them.

Finally, the patients were advised to use paracetamol (500 mg) and/or naproxen (750 mg), if necessary. They were asked not to take analgesics at or 1 day before the follow-up points, as it could affect the clinical outcome measures.

Outcome Measures

All patients were evaluated for primary and secondary outcome measures before injection (baseline) and at 1, 4, and 12 weeks after injection by an investigator blinded to the injections. The primary outcome measure of the study was the Shoulder Pain and Disability Index (SPADI), while the secondary outcome measures were visual analog scale (VAS) scores, active range of motion of the shoulder (ROM), pressure pain thresholds (PPT), and treatment satisfaction. All adverse events that occurred during the procedure and at a follow-up visit were recorded.

Primary outcome measure: The Shoulder Pain and Disability Index is a shoulder-specific index consisting of 13 items that assess shoulder pain and disability on two different scales. Each item is scored between 0 and 10, and the resulting score is converted into a 100-point scale separately for pain, disability, and total score. Increased SPADI scores indicate an increase in patients' shoulder-related pain and disability. Patients with a reduction in the total SPADI score of 18 points or more from baseline to week 12 (the last follow-up) were considered treatment successes. (2). The SPADI has been shown to be valid and reliable in Turkish (3).

Secondary outcome measures: The VAS (0–10 range) was evaluated in each patient for night and activity. An additional VAS assessment was performed 1 h after the injection. Active

shoulder ROM measurements of the patients were performed using a standard manual goniometer. Measurements were made in the supine position, and active forward flexion (FF), abduction (US), internal rotation (IR), and external rotation (ER) were measured. The IR and ER measurements were made with the shoulder abducted at 90°. The PPT measurements were obtained over the middle deltoid, upper trapezius, infraspinatus, and tibialis anterior muscles using a 1 cm diameter probe from an electronic digital display algometer (Commander Echo® Algometer, JTECH Medical, Midvale, UT, USA). Measurements were taken directly on the skin and vertically, and the patient was instructed to stop when the feeling of pressure first turned into a feeling of pain and discomfort. Three measurements were taken from each region, and the average of the last two measurements was recorded. The PPT values were expressed as kilograms per square centimeter (kg/cm²). A low PPT value represents a decrease in the pain threshold and, therefore, increased sensitivity. A 5-point Likert scale was used to evaluate the patients' overall satisfaction with the treatment (1= extremely dissatisfied, 2= dissatisfied, 3=neutral, 4= satisfied, and 5= extremely satisfied).

The patients' compliance with the exercise program was queried at the 4th and 12th weeks after the injection. The patients were asked to choose between "Never did," "I did it occasionally," and "I did it regularly." Finally, they were asked how much they used the paracetamol (500 mg) and naproxen (750 mg) that had been sent home with them after the injection at the 1st, 4th, and 12th weeks. The total amount of drug used was recorded.

Statistical Analyses

The sample size required for the research was calculated via a website (<http://statulator.com/SampleSize/ss2M.html>). In a previous study, the Minimal Clinically Important Difference (MCID) value for SPADI ranged from 8 to 13 points (2). We established our research hypothesis that the clinical results of SSNB at the level of the spinoglenoid notch would not be non-inferior to SSNB at the level of the suprascapular notch. Accordingly, when the non-inferiority margin is -9 and the standard deviation is 15.3; With 80% power and type 1 error 0.05, 36 patients in each group should be recruited. Assuming a 10% dropout rate, 40 patients were planned for each group.

The collected data were statistically analyzed using IBM SPSS ver. 22.0 (IBM Corp., Armonk, NY, USA). All analyses were performed according to the "intention to treat" principle, and the missing data were completed using the single imputation method. The Shapiro-Wilk test, as well as histograms and QQ plots, were used to test whether the data were normally distributed. Analysis results were presented as mean \pm standard deviation for numerical data and as numbers and percentages for categorical data. For numerical data, the differences between groups were compared using the independent samples t-test or the Mann-Whitney U test. Categorical data were analyzed using chi-square tests or Fisher's exact test. In addition, the differences (Δ) between the baseline value of the outcome measures and the values at the follow-up time points were calculated and included in the intergroup comparison. The Friedmann test was used for intragroup comparisons of the changes in outcome measures from baseline to follow-up times. The post hoc Dunn-Bonferroni test was then used for

pairwise comparisons of follow-up times. A P value less than 0.05 was considered statistically significant.

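### The difference in means behind the 36 per group is not tied to a SPADI score, a visit, or raw versus change, and no planned test is set against the 9-point margin

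*Combined protocol and SAP*

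**What the plan says.** All references are to the combined protocol and SAP.

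- **Outcome Measures, primary outcome.** "The primary outcome measure of the study was the Shoulder Pain and Disability Index (SPADI". The index yields separate pain, disability and total scores. It is taken at baseline and "at 1, 4, and 12 weeks after injection by an investigator blinded to the injections". On direction: "Increased SPADI scores indicate an increase in" pain and disability.
- **Outcome Measures, success definition.** "Patients with a reduction in the total SPADI score of 18 points or more from baseline to week 12" count as treatment successes. This is the only place where the total score and week 12 are singled out for an endpoint.
- **Statistical Analyses, sample size.** The calculation applies "when the non-inferiority margin is -9 and the standard deviation is 15.3; With 80% power and type 1 error 0.05" and arrives at 36 per group, or 40 after 10% dropout. The sidedness of the 0.05 is not stated. The hypothesis is "our research hypothesis that the clinical results of SSNB at the level of the spinoglenoid notch" measured against the suprascapular approach; it names no score, visit or metric.
- **Statistical Analyses, tests.** For numerical data, "the differences between groups were compared using the independent samples t-test or the Mann-Whitney U test". Changes from baseline at the follow-up visits "were calculated and included in the intergroup comparison" as well. Significance is P<0.05. The Dunn-Bonferroni step covers only visit pairs within a group. No confidence interval or test is set against the margin.

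**The concern.** A non-inferiority trial needs one identified comparison that carries the margin, the error rate and the power. Here the sample size implies such a comparison, but the analysis section does not contain it.

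Two gaps combine. First, the sized quantity is not linked to a score, a visit, or raw versus change. Second, the tests that are planned ask whether the groups differ. A non-significant difference test does not show that a 9-point deficit is excluded, and a Mann-Whitney test gives no difference in points to hold against 9.

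The stated 5% and 80% therefore belong to no test in the plan. If the visits disagree, or raw and change disagree, nothing says which result answers the non-inferiority question.

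**Working it through.** **1. The plan's own figure.** Inputs from Statistical Analyses: margin 9, SD 15.3, power 80%, alpha 0.05. The true difference is not stated; 0 is assumed.

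n = 2 × SD² × (z_alpha + z_power)² / margin² = 2 × 15.3² × (1.645 + 0.842)² / 9² = 35.7, so 36 per group. Dropout: 36 / 0.9 = 40. Both figures reproduce.

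At one-sided 0.025 the same formula gives 46, so one-sided 0.05 is inferred from the match. With 36 per arm, power at one-sided 0.025 is 69% (noncentral t). The formula is for a continuous mean difference, not a responder rate.

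**2. Candidate comparisons.** Total score: 3 visits × 2 forms (raw, change) = 6. With the pain and disability scores: 3 × 3 × 2 = 18.

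**3. Does the sign of -9 settle the metric?** No. Higher SPADI is worse. A margin of -9 fits a reduction taken as Group 1 minus Group 2, and equally a raw score taken as Group 2 minus Group 1.

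**4. What depends on raw versus change.** Assume equal SDs at baseline and week 12 and a correlation r between them (the documents give neither). Then SD of change = SD of raw × √(2(1 − r)). Power is by noncentral t, with 36 per arm, one-sided 0.05 and a 9-point margin:

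| r | If 15.3 is the raw SD: change SD, power on change | If 15.3 is the change SD: raw SD, power on raw |
|---|---|---|
| 0.3 | 18.1, 67% | 12.9, 90% |
| 0.5 | 15.3, 80% | 15.3, 80% |
| 0.6 | 13.7, 87% | 17.1, 71% |

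Naming a visit and metric therefore secures 80% for an unadjusted test only if 15.3 is the SD of the variable analysed.

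**5. How often the candidates would disagree.** Simulation with no true difference, 36 per arm, and a one-sided 95% limit judged against 9. Assumed: follow-up SD 15.3, between-visit correlation 0.5-0.8, baseline correlation 0.3-0.6.

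- Baseline SD 15.3: raw and change at week 12 conflict in 21-26% of trials; the six comparisons are not unanimous in 42-61%.
- Baseline SD 10: about 15-17% and 33-49%.
- The three raw visits conflict in 22-35%.

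**6. Baseline-adjusted week-12 comparison.** Regressing week 12, or change to week 12, on group and baseline gives the same group difference; only the baseline slope shifts by 1. If 15.3 is the week-12 SD, the residual SD is 15.3 × √(1 − r²) = 14.6 at r = 0.3 and 12.2 at r = 0.6.

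Normal approximation: z = 9 / (residual SD × √(2/36)) − 1.645 = 0.97 and 1.47, which is about 83% and 93% power. Simulation gives 82-92%, with 4.8-5.2% error at a true 9-point deficit. If 15.3 is instead the SD of change, simulated power is 86-92%.

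**The case against.** The strongest reply is that the primary comparison can be read off the page. The 18-point rule stands under the primary-outcome label, uses the total score, and runs from baseline to the last follow-up. This largely stands for score and visit: total SPADI at week 12 is the natural reading, and the gap there is an unstated link. It does not settle raw versus change. The success rule uses a reduction, but it is binary, and the analysis section runs both forms.

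Other points that stand:

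- The conflict rates rest on correlations and SDs that are not in the documents, and they fall when the baseline SD is smaller. Some disagreement is ordinary sampling variation at about 80% power and would persist after the fix; what changes is that one result decides.
- Covariate adjustment is not needed for validity. Unadjusted raw and change comparisons at week 12 each hold about 5% error. Adjustment is preferred because it removes the raw-versus-change choice and adds power.
- The simulations use 36 per arm, whereas 40 are planned and intention-to-treat with single imputation is specified.

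Two stronger readings are tempting. A reader might infer that six tests at P<0.05 inflate the chance of a false non-inferiority claim. Those are difference tests, and their multiplicity is not the non-inferiority error rate. An error of 9-12% arises only if non-inferiority at any one of the three raw visits sufficed, a rule the documents do not contain. A reader might also infer that week 12 and the total score occur nowhere outside the success definition. They do occur elsewhere: week 12 in the visit schedule and in the exercise and drug-use queries, and the total score in the scoring description.

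**Conclusion.** The point holds, and the plan should be changed. The sample-size arithmetic is sound at one-sided 0.05. What is missing is the comparison it belongs to and any analysis that uses the margin; these are two gaps, and closing only one would not be enough.

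That the plan yields no non-inferiority verdict and no rule for conflicting results follows from the text and needs no assumption. The size of the practical effect does rest on assumptions: over baseline SDs of 10 to 15.3 and the correlations above, raw and change at week 12 disagree in roughly 15-26% of trials of equal approaches, and the six total-score results are not unanimous in roughly 33-61%. These are illustrations, not predictions for this trial.

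The documents do not show that a favourable visit or metric was selected, and that should not be inferred.

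**What to change.** - Make total SPADI at week 12 the single primary comparison, subject to sponsor confirmation.
- Estimate the Group 1 minus Group 2 difference in a linear model with baseline total SPADI as a covariate.
- Conclude non-inferiority if the upper one-sided 95% confidence limit is below +9 points.
- State that alpha is one-sided 0.05, and which variable the SD of 15.3 describes. If an unadjusted comparison is kept, name raw or change and give its SD.
- Label weeks 1 and 4, the pain and disability scores, and the 18-point responder rate as secondary.
- If the choice was made after the data were seen, label it post hoc and show all six total-score comparisons together.

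Cost: SAP wording only, since baseline SPADI is already collected. For this one comparison a linear model replaces the t-test or Mann-Whitney test, and the other visits and metrics lose confirmatory status. The text is in the past tense and reports conduct from June 2021 to August 2022. A choice made after seeing the data would not restore the 5% error; in that case the gain is honest labelling.

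### The non-inferiority hypothesis is worded in reverse, the -9 margin is tied to no defined difference, and no planned test uses the margin, so the plan as written cannot establish non-inferiority

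*Combined protocol and SAP*

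**What the plan says.** All the design elements for the primary comparison are in two places.

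- **Hypothesis** (Statistical Analyses, first paragraph): the spinoglenoid block "would not be non-inferior to SSNB at the level of the suprascapular notch".
- **Margin and variability** (same paragraph): the calculation is made "when the non-inferiority margin is -9 and the standard deviation is 15.3". The scale (score or improvement), the order of subtraction and the visit are not given.
- **Error rates and size** (same paragraph): "With 80% power and type 1 error 0.05, 36 patients in each group should be recruited", and then "Assuming a 10% dropout rate, 40 patients were planned for each group". Whether the 0.05 is one-sided or two-sided is not stated.
- **Direction of the primary outcome** (Outcome Measures): "Increased SPADI scores indicate an increase in" pain and disability, so higher is worse. SPADI is measured at baseline and at weeks 1, 4 and 12. Treatment success is a fall in total score of at least 18 points by week 12.
- **Analysis** (Statistical Analyses, second paragraph): groups are compared by t-test or Mann-Whitney test. Changes from baseline also enter the comparison, but their sign is not defined. The only decision threshold is "A P value less than 0.05 was considered statistically significant".

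**The concern.** A non-inferiority trial needs three things to agree: the hypothesis, the margin with its direction, and the rule that compares the data with the margin. Here the first is stated backwards, the second is incomplete and the third is absent.

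Without a rule, a reader cannot tell in advance which result would support the spinoglenoid block. A P value above 0.05 from a test of difference does not show that a 9-point deficit has been excluded, and a P value below 0.05 answers a different question. Because scale, subtraction order, visit and confidence level are all open, they could also be settled after the data are seen.

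**Working it through.** **Inputs.** From Statistical Analyses: margin size 9, SD 15.3, power 80%, type 1 error 0.05, dropout 10%. Assumed because not stated: true difference 0, one-sided test, equal groups (implied by the equal numbers).

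**1. Reproduce the planned size.** n per group = 2 × (SD/margin)² × (z for alpha + z for power)².

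- One-sided 0.05: 2 × (15.3/9)² × (1.6449 + 0.8416)² = 5.78 × 6.183 = 35.7, so 36. With dropout, 36/0.9 = 40. Both stated figures reproduce.
- One-sided 0.025: 5.78 × (1.9600 + 0.8416)² = 5.78 × 7.849 = 45.4, so 46. This does not reproduce.

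The calculation is therefore a non-inferiority calculation at one-sided 0.05, which contradicts the literal hypothesis. The margin is squared, so +9 and -9 give the same n; the sample size cannot reveal the intended direction.

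**2. What -9 means under each definition of the difference.**

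| Difference | If spinoglenoid is 9 points worse | Is -9 the right sign? |
|---|---|---|
| Raw SPADI, spinoglenoid minus suprascapular | +9 | No |
| Raw SPADI, suprascapular minus spinoglenoid | -9 | Yes |
| Improvement (baseline minus follow-up), spinoglenoid minus suprascapular | -9 | Yes |

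The plan does not say which row applies.

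**3. The planned test against a margin-based rule.** Let D be spinoglenoid minus suprascapular raw SPADI. Its standard error is 15.3 × √(2/n): 3.606 at 36 per group and 3.421 at 40.

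- The two-sided t-test is non-significant when the observed D is within ± t(0.975) × SE. At 40 this is 1.991 × 3.421 = 6.81; at 36 it is 1.994 × 3.606 = 7.19.
- Non-inferiority at one-sided 0.05 needs the observed D below 9 - t(0.95) × SE. At 40 this is 9 - 1.665 × 3.421 = 3.31; at 36 it is 9 - 1.667 × 3.606 = 2.99.

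So at 40 per group an observed deficit between 3.31 and 6.81 points is non-significant and yet fails to exclude a 9-point deficit. The two rules are not interchangeable.

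**4. Size of the gap.** With a true D of +9, the noncentrality is 9/3.421 = 2.631 at 40 per group (78 df) and 9/3.606 = 2.496 at 36 (70 df). The noncentral t distribution gives P(two-sided P > 0.05) = 0.262 at 40 and 0.308 at 36. The margin-based rule passes with probability 0.05.

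**5. Power of the margin-based rule at a true difference of 0** (noncentral t).

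| Per group | 90% CI (one-sided 0.05) | 95% CI (one-sided 0.025) |
|---|---|---|
| 36 | 79.6% | 69.2% |
| 40 | 83.2% | 73.8% |

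**The case against.** The strongest reply is that the intent can be recovered. The hypothesis looks like a double-negative slip, the next sentence follows from it as a non-inferiority calculation, and 36 per group reproduces on that basis. This stands as an account of what was meant. It does not supply the missing rule: even with the wording corrected, nothing in the analysis paragraph uses the margin.

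A reader might go further and infer that -9 points the wrong way on a higher-is-worse scale, so that the plan would endorse an inferior block. The documents do not support that. The sign is wrong only for raw SPADI taken as spinoglenoid minus suprascapular. It is right for the reverse subtraction, and right for improvement scores, which is a plausible reading because success is defined as a reduction and changes from baseline are analysed. Requiring the lower limit to exceed -9 on the raw spinoglenoid-minus-suprascapular difference would pass a block truly 9 points worse in more than 99.9% of trials, but no such rule appears in the plan. That figure does not describe this trial.

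It is also fair to say that the plan nowhere states that a non-significant result will be taken as non-inferiority. The 26% and 31% figures are conditional on that reading.

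Finally, the document is written as a completed study, so fixing the visit and confidence level now is a new choice. This stands, and the fix has to declare it.

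**Conclusion.** Wrong as written, on two counts: the hypothesis contradicts the sample-size calculation that follows it, and there is no comparison of a confidence bound with the margin, so the plan cannot establish non-inferiority. The margin's sign is undefined rather than wrong.

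The planned numbers of 36 and 40 per group are sound on their own terms, given one-sided 0.05 and a true difference of 0. The consequence for error rates depends on how a non-significant difference would be interpreted. If it were read as non-inferiority, the false-positive rate at a true 9-point deficit would be about five to six times the intended 5%, assuming SD 15.3 and a t-test on means. The contradiction and the missing test do not depend on that assumption.

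**What to change.** 1. Restate the hypothesis: the spinoglenoid block would be non-inferior to the suprascapular block.
2. Define the difference: mean total SPADI, spinoglenoid minus suprascapular, at one named visit. Week 12 is proposed because Outcome Measures uses it for treatment success; the plan does not itself attach the margin to that visit.
3. State the hypotheses and rule. H0: the difference is +9 or more. H1: it is below +9. Claim non-inferiority only if the upper limit of the two-sided 90% confidence interval is below +9. If improvement (baseline minus follow-up) is used instead, the equivalent rule is that the lower limit of spinoglenoid minus suprascapular exceeds -9.
4. State that type 1 error is one-sided 0.05, the level at which 36 per group reproduces. If a 95% interval is preferred, restate power as about 69% at 36 and 74% at 40 per group.
5. Say that a P value from a test of difference, significant or not, is not the basis for the non-inferiority conclusion.

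The cost is one rewritten paragraph and one confidence interval from data already collected. N is unchanged and no new patients are needed. The downside is that the visit and the confidence level must be reported openly as newly specified choices, and power is less favourable if the 95% interval is chosen.

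### The stated 80% power belongs to a one-sided 5% non-inferiority test that the analysis text does not contain

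*Combined protocol and SAP*

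**What the plan says.** Both parts of the point are in the Statistical Analyses section of the combined protocol and SAP.

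- **Sizing.** The hypothesis sentence says that the spinoglenoid approach "would not be non-inferior to SSNB at the level of the suprascapular notch". The wording is garbled, but the inputs are those of a non-inferiority calculation: "when the non-inferiority margin is -9 and the standard deviation is 15.3". The result follows: "With 80% power and type 1 error 0.05, 36 patients in each group should be recruited". Then: "Assuming a 10% dropout rate, 40 patients were planned for each group". The text does not say whether the 0.05 is one-sided or two-sided, and it does not state the assumed true difference.
- **Analysis.** For numerical data, "the differences between groups were compared using the independent samples t-test or the Mann-Whitney U test". Changes from baseline are also compared between groups. The only decision rule is "A P value less than 0.05 was considered statistically significant". No sidedness, confidence interval or non-inferiority test is given, and the margin is not mentioned again.

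**The concern.** A sample size supports a conclusion only if the analysis uses the test and level for which the size was calculated. Here the sizing paragraph describes one test and the analysis paragraph another, and neither states sidedness.

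Two things are at stake. First, the analysis as written never tests the stated hypothesis, so the stated power cannot apply to it. Second, if a margin comparison is added later, nothing in the text fixes whether a 90% or a 95% interval is used. That choice moves the power by about 10 percentage points. For a band of plausible results it also changes the conclusion, and it could be made after the data are seen.

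**Working it through.** **Inputs from the plan:** margin 9 points (written as -9), SD 15.3, power 80%, type 1 error 0.05, equal groups, 10% dropout. **Assumption, not stated:** true difference 0.

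**1. Reproducing the plan's figure.** n per group = 2 × (z_α + z_β)² × (SD/margin)², with (15.3/9)² = 2.89 and z_β = 0.8416.

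- One-sided 5%: 2 × (1.6449 + 0.8416)² × 2.89 = 35.7, so 36. This is the plan's figure.
- Dropout: 36/0.9 = 40. This is also the plan's figure.
- One-sided 2.5% (the level of a 95% interval): 2 × (1.9600 + 0.8416)² × 2.89 = 45.4, so 46. This does not match the plan.

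The 36 is therefore a one-sided 5% figure.

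**2. Power of a margin comparison, true difference 0.** The standard error is 15.3 × √(2/n), which is 3.61 for n = 36 and 3.42 for n = 40. The noncentrality is 9/3.61 = 2.50 and 9/3.42 = 2.63. From the noncentral t distribution:

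| Interval compared with margin | 36 per group | 40 per group |
|---|---|---|
| 90% (one-sided 5%) | 79.6% | 83.2% |
| 95% (one-sided 2.5%) | 69.2% | 73.8% |

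The normal approximation gives 80.3% and 83.8% in the first row, and 70.4% and 74.9% in the second. For 80% power at one-sided 2.5%, 46 (normal) or 47 (t) evaluable per group are needed, that is 52 or 53 after 10% dropout.

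**3. What the planned difference test does.** Its null hypothesis is zero difference, not a 9-point disadvantage. If the true difference is 0, as the sizing assumes, a two-sided test gives P<0.05 about 5% of the time by construction. A P value above 0.05 shows only that zero was not excluded. With 36 per group, an observed disadvantage must exceed 1.994 × 3.61 = 7.2 points to reach two-sided P<0.05. Non-inferiority by a 90% interval already fails once the disadvantage exceeds 9 − 1.667 × 3.61 = 3.0 points. Between about 3.0 and 7.2 points, the planned test would find no significant difference although non-inferiority had not been shown.

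**4. Where the interval level changes the conclusion.** With 36 per group and SD 15.3, the half-width is 6.0 points for a 90% interval and 7.2 for a 95% interval. The largest observed disadvantage that still clears the margin is 9 − 6.0 = 3.0 or 9 − 7.2 = 1.8 points. A disadvantage between about 1.8 and 3.0 points passes with one interval and fails with the other.

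**The case against.** The strongest reply is that nothing has been miscalculated. A non-inferiority test is one-sided by nature. Read that way, both 36 and 40 reproduce exactly, and one-sided 5% is a choice of convention against which the documents cite no rule. All of this stands. A reader might infer that 36 is an arithmetic error or that the enrolment must rise, and the documents support neither.

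A reader might also infer that the trial's real power is 69% because the analysis uses two-sided P<0.05. That goes too far, for three reasons.

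- The plan does not say that its tests are two-sided. This is the ordinary reading of a plain t-test at P<0.05, but it remains an inference.
- The 69% arises in only two settings: a 95% interval compared with the margin when the true difference is 0, or a two-sided difference test when the true difference is 9. The plan contains no such interval and assumes no such difference. The two settings share a noncentrality value but answer different questions.
- The plan specifies intention to treat with single imputation, so 40 per group would nominally be analysed, which gives 74% at that level. Imputed values add no real information, so 69% remains the fair figure if dropout reaches 10%.

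Finally, it can be said that the remedy is only wording. That is true of its cost. But the missing wording is the primary test itself, so the gap is more than an omitted detail.

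**Conclusion.** The point holds as a mismatch between sizing and analysis. The stated 36 per group with 80% power is right for a non-inferiority test at one-sided 5% with margin 9, SD 15.3 and true difference 0. The plan does not state that level, and its analysis section holds only difference tests with no reference to the margin. Followed as written, the analysis delivers neither the stated power nor a test of non-inferiority.

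Once a margin comparison is added, the size of the issue depends on the level: about 80% (36 evaluable per group) to 83% (40) with a 90% interval, or about 69% to a nominal 74% with a 95% interval. At 36 per group, the type II error with a 95% interval is about 31%, against the planned 20%. These figures assume that the SD of 15.3 applies to the SPADI quantity analysed and that the true difference is zero.

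**What to change.** Change two sentences in Statistical Analyses and leave the enrolment as it is.

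- **Sizing text:** state that the 0.05 is one-sided and that the assumed true difference is zero. Give the power as about 80% with 36 evaluable per group and 83% with 40.
- **Analysis text:** define the primary SPADI analysis as the between-group difference with a 90% confidence interval. Non-inferiority is concluded if the bound on the side unfavourable to the spinoglenoid approach lies within the 9-point margin. State the direction of the difference so that the sign of the margin is clear. The P<0.05 difference tests may stay for other comparisons, but not as the basis for the non-inferiority conclusion.
- **If a 95% interval is preferred:** use it in both places and restate the power as about 69% with 36 evaluable per group (nominally 74% with 40). Attach these figures to the interval, never to the P<0.05 difference test.

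The first option costs only wording and keeps the stated power. The second costs about 10 points of stated power. Neither needs more patients.
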